6.5 Concomitant Therapy

Concomitant medications will be recorded on the case report form (CRF), which includes all FDA-approved medications and therapies.

6.6 Blinding and Unblinding

Subjects will be randomized into active treatment groups and study personnel will be blinded to treatment assignments. The designated cell-processing technicians will prepare the investigational product for infusion. The investigational agent infusions will be prepared in identical infusion bags and labeled with the identical investigational drug labels as to preserve the blind. The designated technicians in the ISCI Cell Processing Laboratory (CPL) or designee will be responsible for maintaining the investigational product records including randomized treatment assignments by subject identification.

If for important medical reasons unblinding is thought to be necessary, the Investigator may identify the treatment assignment by obtaining the randomization assignment by contacting the Director of the Cell Manufacturing Program at ISCI who is responsible for maintaining randomization records for all subjects.

6.7 Study Investigational Therapy Management

6.7.1 Investigational Product Labeling and Storage

The product label contains the elements required by the CFR and other national and local authorities for investigational products. ISCI GMP Cell Processing Facility will directly store and deliver the designated cell processing technologist in the CPL, and will be kept cryopreserved in liquid nitrogen vapor phase until shortly before administration. Investigational product must be stored in a securely locked enclosure. Access is strictly

limited to unblinded CPL personnel prior to preparation for infusion. After preparation for infusion, the Investigator and his or her designees are permitted to administer the Investigational Product only to subjects participating in this protocol.

6.7.2 Investigational Product Accountability Procedures

In accordance with all applicable regulatory requirements, the Cell Processing Laboratory will maintain a record of the investigational products hMSCs received, dispensed, administered, destroyed, or returned. The final disposition of all unused, empty, and partially used Cryocyte™ bags will be handled in accordance with the drug preparation manual.

7 STUDY PROCEDURES

Time and Events Schedule

The Time and Events Schedule for the conduct of this study is shown in Table 1

Schedule of Assessments

| Table 1: Time and Events Table VISIT | | Screening | Baseline | Day 0 Infusion | Week 2 Post-Infusion | Month 1 Post-Infusion | Month 3 Post-Infusion | Month 6 Post-Infusion | Month 12 Post-Infusion |
|--|---------------------------------|--------------------------------|---------------------|---------------------|----------------------|-----------------------|-----------------------|-----------------------|------------------------|
| | | Within 7 days Pre or Post-Cath | 0-30 days post-Cath | 0-30 days post-Cath | ± 5 days | ± 2 weeks | ± 2 weeks | ± 2 weeks | ± 2 weeks |
| Informed Consent ¹ | | X | | | | | | | |
| Medical History | | X | | | | | | | |
| Physical Exam & Vital Signs ² | | X | | X | X | X | X | X | X |
| 12-lead Electrocardiogram (ECG) | | X | | X | | X | X | X | X |
| Concomitant Medications ³ | | X | X | X | X | X | X | X | X |
| Randomization ⁴ | | | X | | | | | | |
| IV Infusion Treatment ⁵ | | | | X | | | | | |
| Coronary Angiogram ⁶ | | X | | | | | | X | |
| FFR, CFR, IFR, IVUS, and/or OCT (optional) ⁷ | | X | | | | | | X | |
| Brachial Artery Ultrasound ⁸ | | | X | | X | X | X | X | |
| Bone Marrow Biopsy ⁹ | | | | | | | X | | |
| Questionnaires ¹⁰ | | | X | | X | X | X | X | |
| Review Adverse Events | | | X | X | X | X | X | X | X |
| Laboratory Testing ¹¹ | Hematology & Chemistry | X | | X | | X | X | X | |
| | Coagulation | X | | | | | X | X | |
| | Urinalysis | X | | | | | X | X | |
| | HbA1c | X | | | | | X | X | |
| | Biomarkers (SST) (includes PRA) | | X | | X | X | X | X | |
| | Immune Monitoring (MNC) | | X | | X | X | X | X | |
| | Genetic Testing (DNA and RNA) | | | X | | | | X | |
| | EPC-CFU assay | | X | | X | X | X | X | |
| | Viral Serology | X | | | | | | | |
| | Serum Pregnancy Test | X | | X | | | | | |

Time and Events Table Key:

1. Informed consent can be obtained Pre- or Post- cardiac catheterization. The first angiogram is clinically indicated.
2. A physical examination will be performed and may include the following examinations: general appearance; skin and nails; limbs; head, eyes, ears, nose, throat (HEENT) and neck; respiratory; cardiovascular; and abdominal. Vital Signs measurements will consist of: height, weight, heart rate, blood pressure, respiratory rate, oxygen saturation, and temperature. Height is only required at screening. If physical exam and vitals were performed as “Standard of Care” within 7 days of signing ICF, those results may be extracted from patient medical records and used for the screening visit in this study. The screening visit physical exam can be completed by the participants’ treating physician.
3. Concomitant medications will be recorded at screening visit and updated at each visit.
4. Randomization can be performed within 7 days prior to IP infusion.
5. Refer to Appendix 1 for Infusion guidelines.
6. Refer to hospital protocols for coronary angiogram guidelines. Results from the screening cardiac catheterization may be extracted from patient medical records and used for the purposes of this study. Subjects who did not have a stent placed at screening will not undergo the coronary angiogram (and associated measurements) at Month 6, but should complete the other assessment listed on Time and Events Table, per investigator’s judgement.
7. Subjects who did not have a stent placed at screening may still undergo the coronary angiogram (and associated measurements) at Month 6, but should complete the other assessment listed on Time and Events Table. All procedures (CFR, FFR, IFR, IVUS, and/or OCT) will be performed in accordance with the established hospital protocols which are done as “Standard of Care”. Subjects who undergo PCI at screening should have CFR, FFR, IFR, IVUS, and/or OCT measurements if available, as per investigator’s judgement.
8. Refer to Appendix 2 for Brachial Ultrasound (Brachial Artery Ultrasound to assess endothelial function must be performed prior to 12pm).
9. Bone Marrow Biopsy will be performed at month 3 visit. Separate ICF will be used for this optional sub-cohort. The bone marrow biopsy can be performed in the Catheterization Laboratory or in Interventional Radiology department, either with or without imaging guidance (X-Ray or Ultrasound).
10. All subjects will be asked to complete the Seattle Angina Questionnaire (SAQ), EQ-5D, and SF-36 quality of life questionnaires. Only male subjects will be asked to

complete the IIEF questionnaire, and only female subjects will be asked to complete the SQOL-F questionnaire.

11. Subjects must be fasting for at least 8 hours prior to blood collection as required by standard of care. If labs were performed as “Standard of Care” within 7 days of signing ICF, those results may be extracted from patient medical records and used for the screening visit in this study. The minimal laboratory requirements include:

Hematology Tests:

Complete Blood Count with Differential (WBC, RBC, hemoglobin, hematocrit, MCV, and platelets; Diff: neutrophils, lymphocytes, monocytes, eosinophils, and basophils).

Chemistry Tests: (fasting required)

Comprehensive Metabolic Panel (glucose, sodium, potassium, chloride, bicarbonate, blood urea nitrogen, creatinine, total protein, albumin, alkaline phosphatase, total bilirubin [fractionate if total >1.5 times normal], alanine transaminase (ALT), aspartate transaminase (AST), and GFR).

Coagulation Tests: Prothrombin time (PT/INR), activated partial thromboplastin time (aPTT).

Urinalysis: Routine Urinalysis with reflex to culture.

Glycosylated Hemoglobin: HbA1c

Biomarkers: SST: (2 Gold or Tiger top serum separator tubes) Transcriptomic/proteome (RNA, mRNA, protein samples, and telomerase, akt); growth factors (sdf-1, notch); functional assays (cell-growth rate, VEGF, and CFU assays), PRA, and more.

Immune monitoring: MNCs: (2 Green top sodium heparin tubes) CD3*CD25* or CD3*CD69* and more.

Gene Expression: peripheral blood will be collected prior to infusion on Day 0, and at the 6 month follow up visit to analyze DNA & RNA (DNA to be collected at one time point only).

EPC-CFU Assay: Blood samples (5 Lavender top tubes) to measure Endothelial Progenitor Cell-Colony Forming Units (EPC-CFU).

Viral Serology: Infectious disease tests – HIV, HIV 2, Hep B (HBsAg), Hep C (Anti-HCV), and CMV.

Serum Pregnancy Test: Serum β HCG test will be completed at screening and within 36 hours prior to infusion in women of childbearing potential only.

If subjects are unable to come to the site for specified visits alternative methods for assessments (e.g., phone contact, virtual visit, alternative location for assessments, including local labs or imaging centers) could be implemented when necessary.

8 Study Phases and Visits

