| STUDY OBJECTIVES | 
Test the hypothesis that intravenous (IV) delivery of MSCs improves coronary artery endothelial function (assessed by fractional flow reserve (FFR) and coronary flow reserve (CFR) at 6 months), systemic endothelial function (assessed by FMD and EPC-colony assay), and angina symptoms (assessed by Seattle Angina Questionnaire) in type 2 diabetic patients with symptomatic IHD compared to placebo.
 
Test the hypothesis that allogeneic MSCs promote systemic and coronary endothelial repair through rescue of bone marrow progenitors in type 2 diabetic patients with symptomatic IHD compared to placebo.
 |
| STUDY DESIGN | Randomized, Double Blind, Placebo controlled, Pilot Trial |
| INVESTIGATIONAL PLAN | 
30 type 2 diabetic patients with symptomatic IHD that undergo standard-of-care coronary angiography with or without Percutaneous Coronary Intervention (PCI) and meet all the inclusion and none of the exclusion criteria will be randomized to receive, within 2 weeks post- standard-of-care coronary angiography , either allogeneic MSCs or placebo in a 1:1 blinded fashion:
 
Group A (15 subjects): Allogeneic MSCs Fifteen (15) subjects will be treated with a single administration of intravenous allogeneic hMSCs (100 million).
 
Group B (15 subjects): Placebo (Cell-free PlasmaLyte-A medium supplemented with 1% HSA) Fifteen (15) subjects will be treated with intravenous placebo infusion.
 
 - Patients will be followed for scheduled outcome and safety assessments at 1, 3 and/or 6 months and 12 months post-infusion. - A bone marrow biopsy will be obtained from participants in a sub-study at the 3-month follow up for cellular and molecular studies (separate informed consent document). |
| ROUTE OF ADMINISTRATION | Peripheral Intravenous Infusion |
| DURATION OF STUDY PARTICIPATION | 12 months |
| SUBJECT POPULATION | 30 subjects age >18 with type 2 diabetes and symptomatic IHD with an indication for standard-of-care coronary angiography with or without PCI |

| | |
|-------------------------|---|

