damaged endothelial cells by stem/progenitor cells could allow reendothelialization, as well as neovascularization of ischemic tissues.

Follow-up coronary angiography after PCI is commonly implemented to assess the efficacy and safety of new revascularization devices and novel therapies. However, in clinical practice, routine follow-up coronary angiography has not been considered indicated in stable or asymptomatic post-PCI patients because the direct clinical benefits have been poorly defined. To address this question, Misumida et. al.[48], conducted a systematic review and meta-analysis of randomized trials to assess the potential clinical benefits associated with routine follow-up angiography post-PCI. They compared clinical outcomes after PCI between patients who underwent routine follow-up coronary angiography and those who only had clinical follow-up. Five randomized trials, totaling 4,584 patients met the inclusion criteria, including studies that used sub-randomization and ones that assigned consecutive patients per study protocol. The results showed that routine follow-up coronary angiography was associated with a lower rate of myocardial infarction (odds ratio [OR] 0.65; 95% confidence interval [CI] 0.46–0.91; $P=0.01$) without reduction in all-cause mortality (OR 0.87; 95% CI 0.59–1.28; $P=0.48$), and a higher rate of target lesion revascularization (OR 1.73; 95% CI 1.42–2.11; $P<0.001$). The investigators concluded that further studies investigating the potential role of routine follow-up angiography may be warranted.

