8.2 Baseline and Day 0 Visit

See Table 1 for the procedures and assessment to be performed during the baseline visit of the study. This visit will occur after all screening tests are completed and it has been determined that the subject meets eligibility criteria. This visit should occur within 0 - 30 days post-coronary angiogram.

See Table 1 for the procedures and assessment to be performed during the Day 0 visit of the study. The Day 0 visit will occur within 0 - 30 days post-coronary angiogram after all baseline tests are completed and it has been determined that the subject remains eligible. Once the subject is deemed eligible to continue in the study, the subject will be administered the investigational product. Refer to Appendix 1 for Infusion Guidelines.

8.3 Week 2, Month 1, Month 3, Month 6, and Month 12 (Post-Infusion Visit)

See Table 1 for the procedures and assessment to be performed for the Week 2, Month 1, Month 3, Month 6, and Month 12 study visits. Subjects who had a stent placed at screening will have a follow up coronary angiography at 6 months post-investigational product infusion to evaluate the treated lesion lumen loss with quantitative coronary angiography (QCA), physiology with fractional flow reserve (FFR) and endothelial function with coronary flow reserve (CFR). Outpatient visits should be completed as close to the scheduled visit dates as possible. There will be a window of ± 5 days for week 2 and ± 2 weeks for the Month 1, 3, 6, and 12 study visits.

An optional sub-study will be conducted on at least 5 participants from each treatment group in which they will undergo a bone marrow biopsy at Month 3 for a detailed molecular (genomic, proteomic, proliferation, senescence and differentiation assays) and functional assessment (angiogenic assays) of the effect of allogeneic MSCs on bone marrow derived autologous MSC and EPCs. All subjects will be asked to sign a separate ICF before participating in this optional sub-study. Due to the blinded nature of the study, more than 10 subjects will be enrolled in this sub-study and Cell Manufacturing lab will inform the clinical team once 5 subjects from each treatment complete the bone marrow biopsy. In the interest of participant safety, the bone marrow biopsy may be performed under ultrasound guidance (X-Ray or Ultrasound) by interventional radiology department, if indicated by investigator's clinical judgement.

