8.4.4 Coronary Angiography

Coronary angiography will be done by the interventional cardiologist 6 months after infusion of the investigational product to assess post-PCI coronary artery endothelial function, assessed by IFR, CFR, and/or FFR, as available. Participants will also have evaluation of target lesion lumen loss by IVUS or OCT, as available.

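### Table 1 notes 6 and 7 conflict on the Month 6 coronary angiogram in subjects not stented at screening; minor: the primary objective names measures ranked as secondary endpoints

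*Combined protocol and SAP*

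**What the plan says.** **Month 6 angiogram.** In the key to Table 1 (Section 7), note 6 states: "Subjects who did not have a stent placed at screening will not undergo the coronary angiogram (and associated measurements) at Month 6". Note 7, attached to the row for FFR, CFR, IFR, IVUS and OCT, states: "Subjects who did not have a stent placed at screening may still undergo the coronary angiogram (and associated measurements) at Month 6". The synopsis and its subject-population entry admit patients whether or not they have PCI.

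Two other sections deal with this angiogram. Section 8.3 says: "Subjects who had a stent placed at screening will have a follow up coronary angiography at 6 months post-investigational product infusion". Section 8.4.4 says: "Coronary angiography will be done by the interventional cardiologist 6 months after infusion of the investigational product to assess post-PCI coronary artery endothelial function", with that function "assessed by IFR, CFR, and/or FFR, as available".

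Note 1 says of the screening procedure: "The first angiogram is clinically indicated". The Background (1.1) discusses follow-up angiography in patients who have had PCI and says of ordinary care: "routine follow-up coronary angiography has not been considered indicated in stable or asymptomatic post-PCI patients because the direct clinical benefits have been poorly defined". Section 12.5 pays an additional $50 to subjects catheterized at Month 6.

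**Objectives, endpoints and analysis.** Section 2.1.1 puts FFR, CFR, FMD, the EPC colony assay and the SAQ into the primary objective. Section 2.2.1 makes only FMD% and EPC-CFUs primary endpoints. Section 2.2.2 lists CFR/FFR and the SAQ scales as secondary. Section 10.1 includes all randomized subjects in the efficacy summaries and defines no coronary subset. Section 10.2 calls the efficacy outcomes exploratory and makes no multiplicity adjustment.

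**The concern.** One note forbids a procedure and the next allows it, for the same subjects at the same visit. The procedure is a cardiac catheterization, so this matters more than a scheduling slip. Staff who follow note 7 would depart from note 6. The subject would also undergo an invasive test for which the protocol gives no rationale in people without PCI.

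There is a statistical consequence too. If measurement in unstented subjects is discretionary six months after infusion, the population for the Month 6 coronary comparison is not set in advance. It depends on who happened to be catheterized.

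The objective mismatch is a smaller matter. A reader of 2.1.1 would expect coronary function and angina to be primary measures, and they are not.

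**Working it through.** The plan states no figure on this point, so the check is a comparison of texts.

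1. **Do the notes address the same case?** The population (no stent placed at screening), the procedure (the coronary angiogram with its associated measurements) and the visit (Month 6) all match. Note 6 prohibits and note 7 permits. Both cannot hold.

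2. **Do the notes reconcile themselves?** Note 6 ends with a reference to investigator judgement, but it follows the clause on completing the other assessments and most naturally qualifies that clause. The standard-of-care sentence in note 7 describes how the measurements are performed, not who is eligible. Nothing in note 7 confines its permission to a repeat angiogram needed on clinical grounds.

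3. **Does another section settle it?**
   - 8.3 schedules the angiogram for stented subjects and is silent on the rest.
   - 8.4.4 gives a post-PCI purpose but no restriction.
   - 2.2.2 limits the OCT and target vessel failure endpoints to subjects who have PCI. It puts no such limit on CFR/FFR.
   - 12.5 pays any subject catheterized at Month 6.

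   The first two lean towards note 6. None states a rule for unstented subjects.

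4. **Is the Month 6 angiogram study-driven?** Only the first is called clinically indicated, the second carries its own payment, and the Background says routine follow-up is not considered indicated in stable post-PCI patients. That it is study-driven is an inference from these three points; the protocol does not say so. The Background rationale covers post-PCI patients only.

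5. **What happens to the comparison?** Table 1 places randomization at the Baseline visit, and 8.2 puts that visit after the angiogram and completed screening. Stent status at screening is therefore fixed before randomization, and comparing arms among stented subjects is a comparison within a baseline subgroup. Under note 7 the measured set is the stented subjects plus any unstented subjects chosen at Month 6. That choice may follow symptoms, which the trial hopes to change (SAQ). Entry to the analysis could then depend on treatment even with the blind intact.

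6. **Objective against endpoints.** Section 2.1.1 names five measures and 2.2.1 makes two of them primary: 5 − 2 = 3 (FFR, CFR, SAQ), all ranked secondary in 2.2.2. The synopsis gives the same objective without a primary or secondary label.

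The number of subjects without a clear rule is 30 minus the number stented at screening. The protocol gives no expected stented share, so no count follows.

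**The case against.** The strongest reply is that note 7 is a drafting slip. Its permission is followed by a clause telling subjects to complete the other assessments, which reads like a mis-edited copy of note 6. The row is marked optional, and 8.3 and 8.4.4 point the same way as note 6. That is a fair account of the likely intent, and it supports the fix proposed here. It does not remove the written permission. The conflict is also forbidden against allowed, not forbidden against required.

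The Background is not one-sided either. The meta-analysis it cites reports fewer myocardial infarctions with routine follow-up angiography (odds ratio 0.65), alongside more target lesion revascularization (1.73). That stands, but it concerns patients after PCI and says nothing about unstented subjects.

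Three stronger readings are tempting and are not supported:

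- **PCI without a stent is left without a rule of its own.** Such a subject had no stent placed, so notes 6 and 7 both apply. The conflict covers them; there is no separate gap.
- **The broad primary objective inflates the chance of a false benefit claim.** That needs a rule under which success on any one measure suffices. Section 2.1.1 joins its measures with *and* and states no decision rule. Each primary endpoint is also assessed at four post-infusion visits, so counting one test per measure would misdescribe the plan. No error rate can be derived from the text.
- **Section 10.1 is wrong to include all randomized subjects.** Including them in summaries is compatible with a measurement that is missing or not applicable. The gap is only that no coronary population is named.

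**Conclusion.** Wrong as written. The protocol both forbids and permits a Month 6 coronary angiogram in subjects not stented at screening, and no other section decides between the two. Such subjects are expected because enrolment does not require PCI. The finding rests on the wording alone. The additional weight given to it rests on the inference that the Month 6 procedure is study-driven.

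Its size cannot be put in subjects or in precision, because both depend on a stented share that the documents do not give. It is worth correcting because the procedure is invasive and the coronary comparison needs a population fixed in advance.

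The mismatch between 2.1.1 and the endpoint lists is real but minor. FMD and EPC colonies appear in both places, and 10.2 declares efficacy exploratory, so this is an alignment error and not the loss of a confirmatory test.

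**What to change.** 1. **One rule for the angiogram.** Delete the permissive sentence in note 7. State in 8.4.4 that the Month 6 angiogram is done only in subjects stented at screening. Add the same restriction to the Month 6 CFR/FFR/IFR endpoint in 2.2.2 and in the synopsis. State in 10.1 that Month 6 coronary endpoints are compared by randomized arm in that subgroup, which is fixed before randomization.

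   If the sponsor does want unstented subjects studied, correct note 6 and 8.3 instead, give the rationale and say who is eligible. The coronary analysis set in 10.1 must then be defined to match that choice, not limited to stented subjects.

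2. **Align the objectives.** Limit 2.1.1 to FMD% and EPC-CFU. Add a separate secondary objective for coronary function (FFR/CFR) and angina (SAQ). They do not fit the existing 2.1.2, which concerns rescue of bone marrow progenitors. Label the synopsis objectives to match.

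The changes are to wording, with no added patients or procedures. They need a protocol amendment with written IRB approval before use (12.2). If the consent form changes as well, ongoing subjects must be re-consented (12.3). The scientific price of the preferred rule is that unstented subjects supply no Month 6 coronary data.
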